#### 4.4 End of Study Definition

The end of study treatment period will be announced when the targeted number of primary endpoint events has occurred, unless the study is terminated early because of a recommendation of the DMC.

After notification of study end, an EOS Visit should be scheduled as soon as possible (but within 4 weeks at the latest) for all participants still participating in the study, to determine whether the participant had an event for inclusion in the primary or secondary endpoints.

The date on which the final participant performed the EOS visit is defined as the primary completion date (see schema in Section 1.2).

Participants still on treatment will stop study intervention treatment at the EOS Visit and must perform the PT Visit 30 +5 days after their last dose of study intervention.

Participants no longer taking study intervention must also be contacted as soon as possible after issue of the notification of end of study and be asked to attend the EOS Visit.

For participants who have objected to releasing further information after withdrawing from the study, an updated vital status should be obtained by the investigator from publicly available data sources, wherever allowed by local regulations. The collection of vital status must be obtained within the timelines provided by the sponsor at this time.

The end of the trial as a whole is defined as the date of the last PT Visit of the last participant in the trial globally.

## 5. Study Population

Patients with a diagnosis of HF, NYHA class II–IV, and documented LVEF of  $\geq 40\%$ .

Prospective approval of protocol deviations to recruitment and enrollment criteria, also known as protocol waivers or exemptions, is not permitted.

### 5.1 Inclusion Criteria

Participants are eligible to be included in the study only if all of the following criteria apply:

#### Age

1. Participant must be aged 40 years and older, at the time of signing the informed consent.

#### Type of Participant and Disease Characteristics:

2. Diagnosis of heart failure with NYHA class II–IV, ambulatory or hospitalized primarily for heart failure (if a hospitalized patient cannot be randomized as an in-patient, randomization as soon as possible after discharge is encouraged)
3. On diuretic treatment for at least 30 days prior to randomization
4. Documented LVEF of  $\geq 40\%$  measured by any modality within the last 12 months, at the latest at screening; if several values are available, the most recent one shall be reported. If LVEF was not measured in the past 12 months, a new measurement may be done at screening
5. Structural heart abnormalities based on any local imaging measurement within the last 12 months, latest at screening, defined by at least 1 of the following findings:
  - o LAD  $\geq 3.8\text{cm}$ , LAA  $\geq 20\text{cm}^2$ , LAVI  $> 30\text{ mL/m}^2$ , LVMI  $\geq 115\text{ g/m}^2$  ( $\text{♂}$ ) /  $95\text{ g/m}^2$  ( $\text{♀}$ ), septal thickness or posterior wall thickness  $\geq 1.1\text{ cm}$
6. NT-proBNP  $\geq 300\text{ pg/mL}$  (BNP  $\geq 100\text{ pg/mL}$ ) in sinus rhythm and patient does not have an ongoing diagnosis of paroxysmal atrial fibrillation or NT-proBNP  $\geq 900\text{ pg/mL}$  (BNP  $\geq 300\text{ pg/mL}$ ) in atrial fibrillation (or if atrial fibrillation status is unknown or if patient has an ongoing diagnosis of paroxysmal atrial fibrillation; see Section 4.1) for participants  obtained at the following time:
  - o **Within 90 days prior to randomization** if patient had been **hospitalized for HF** requiring initiation or change in HF therapy or if patient had an **urgent visit for HF** requiring intravenous (IV) diuretic therapy, both within 90 days prior to randomization

OR

- o **Within 30 days prior to randomization** if patient has **not** been hospitalized for HF nor had an urgent HF visit within the past 90 days.

 If a participant is being treated with Entresto (sacubitril/valsartan), the NT-proBNP value only (not BNP) should be used.

**Sex**

7. Male or female.

Women of childbearing potential can only be included in the study if a pregnancy test is negative at screening and baseline and if they agree to use adequate contraception which is consistent with local regulations regarding the methods for contraception for those participating in clinical trials.

**Informed Consent**

8. Capable of giving signed informed consent as described in Section 10.1.3 which includes compliance with the requirements and restrictions listed in the informed consent form (ICF) and in this protocol.

**5.2 Exclusion Criteria**

Participants are excluded from the study if any of the following criteria apply:

**Medical Conditions**

1. eGFR <25 mL/min/1.73 m^2 at either screening or randomization visit.  
NOTE: one reassessment of eGFR is allowed at the screening and randomization visit, respectively
2. Serum/plasma potassium >5.0 mmol/L at either screening or randomization visit.  
NOTE: one reassessment of potassium is allowed at the screening and randomization visit, respectively
3. Acute inflammatory heart disease, e.g. acute myocarditis, within 90 days prior to randomization
4. Myocardial infarction or any event which could have reduced the ejection fraction within 90 days prior to randomization
5. Coronary artery bypass graft surgery in the 90 days prior to randomization
6. Percutaneous coronary intervention in the 30 days prior to randomization
7. Stroke or transient ischemic cerebral attack within 90 days prior to randomization
8. Probable alternative cause of participants' HF symptoms that in the opinion of the investigator primarily accounts for patient's dyspnea such as significant pulmonary disease, anemia or obesity. Specifically, patients with the below are excluded:
  - Severe pulmonary disease requiring home oxygen, or chronic oral steroid therapy
  - History of primary pulmonary arterial hypertension
  - Hemoglobin <10 g/dl\*
  - Valvular heart disease considered by the investigator to be clinically significant
  - Body mass index (BMI) >50 kg/m^2 at screening
9. Systolic blood pressure (SBP) ≥160 mmHg if not on treatment with ≥3 blood pressure lowering medications or ≥180 mmHg irrespective of treatments on 2 consecutive measurements at least 2-minute apart, at screening or at randomization

10. Life-threatening or uncontrolled arrhythmias at screening and/or randomization including but not limited to sustained ventricular tachycardia and atrial fibrillation, or atrial flutter with resting ventricular rate >110 bpm
11. Symptomatic hypotension with mean systolic blood pressure <90 mmHg at screening or at randomization
12. Any primary cause of HF scheduled for surgery, e.g. valve disease such as severe aortic stenosis or severe mitral regurgitation by the time of screening or randomization
13. History of peripartum cardiomyopathy, chemotherapy induced cardiomyopathy, viral myocarditis, right heart failure in absence of left-sided structural disease, pericardial constriction, genetic hypertrophic cardiomyopathy, or infiltrative cardiomyopathy including amyloidosis
14. Presence of left ventricular assist device by the time of screening or randomization
15. History of hyperkalemia or acute renal failure during MRA treatment for >7 consecutive days, leading to permanent discontinuation of the MRA treatment
16. Pregnant or nursing (lactating) women, where pregnancy is defined as the state of a female after conception and until the termination of gestation, confirmed by a positive human chorionic gonadotrophin urine or serum test
17. Known hypersensitivity to the study intervention (active substance or excipients)
18. Hepatic insufficiency classified as Child-Pugh C at screening or randomization\*
19. Addison's disease.

\* *Assessment of relevant laboratory parameters is only required if there is a clinical suspicion of anemia (as an alternative cause of HF symptoms) or hepatic insufficiency.*

### Prior/Concomitant Therapy

20. Requirement of any IV vasodilating drug (e.g. nitrates, nitroprusside), any IV natriuretic peptide (e.g. nesiritide, carperitide), any IV positive inotropic agents, or mechanical support (intra-aortic balloon pump, endotracheal intubation, mechanical ventilation, or any ventricular assist device) within 24 hours prior to randomization
21. Participants who require treatment with **more than one** ACEI, ARB or angiotensin-receptor neprilysin inhibitor (ARNI), or **two simultaneously at randomization**
22. Continuous (at least 90 days) treatment with an MRA (e.g. spironolactone, eplerenone, canrenone, esaxerenone) within 12 months prior to screening. Last intake at least 30 days before randomization. Treatment with MRA should not be interrupted with the purpose of enrollment into the study
23. Concomitant treatment with any renin inhibitor or potassium-sparing diuretic that cannot be stopped prior to randomization and for the duration of the treatment period
24. Concomitant systemic therapy with potent cytochrome P450 isoenzyme 3A4 (CYP3A4) inhibitors (e.g. itraconazole, ritonavir, indinavir, cobicistat, clarithromycin) or

moderate or potent CYP3A4 inducers, that cannot be discontinued 7 days prior to randomization and for the duration of the treatment period.

### Other Exclusions

25. Any other condition or therapy, which would make the participant unsuitable for this study and will not allow participation for the full planned study period (e.g. active malignancy or other condition limiting life expectancy to less than 12 months)
26. Previous assignment to treatment during this study
27. Participation in another interventional clinical study (e.g. Phase 1 to 3 clinical studies) or treatment with another investigational medicinal product within 30 days prior to randomization
28. Close affiliation with the investigational site; e.g. a close relative of the investigator, dependent person (e.g. employee or student of the investigational site)
29. Known current alcohol and/or illicit drug abuse that may interfere with the participant's safety and/or compliance at the discretion of the investigator
30. Participant is in custody by order of an authority or a court of law.

### 5.3 Lifestyle Considerations

No restrictions during the study are required other than those specified in 'Other Exclusions'.

### 5.4 Screen Failures

Screen failures are defined as participants who consent to participate in the clinical study but are not subsequently randomly assigned to study intervention. A minimal set of screen failure information is required to ensure transparent reporting of screen failure participants to meet the Consolidated Standards of Reporting Trials (CONSORT) publishing requirements and to respond to queries from regulatory authorities. Minimal information includes demography, screen failure details (including reason), and eligibility criteria.

If a participant is not eligible during the Screening period for this study (20103), the participant may be rescreened once at a later time, provided the investigator believes that a change in the participant's condition makes him/her potentially eligible.

If a participant was eligible but could not be randomized due to exceptional logistical reasons (e.g. pandemic-related disruption), the participant may be re-screened once.

The following conditions are pre-requisites of re-screening:

1. Before re-screening, new written informed consent must be obtained
2. Allocation of a new participant number
3. All assessments for the study must be repeated
4. At least 3 months between initial screening and rescreening (except in the event of a participant being re-screened for exceptional logistical reasons).

## 6. Study Intervention

Study intervention is defined as any investigational intervention(s), marketed product(s), placebo, or medical device(s) intended to be administered to a study participant according to the study protocol.

### 6.1 Study Intervention(s) Administered

The IxRS will determine the medication numbers for the study site investigator or designee to select for the participant.

Eligible participants will receive study intervention at the doses illustrated in [Table 6-1](#), dispensed as outlined in the SoA (Section [1.3](#)). The dose of finerenone will depend on the eGFR value at the Baseline Visit (determined by the local laboratory):

1. Participants with an eGFR  $\leq 60$  mL/min/1.73m^2 will start with 10 mg (dose level 1) and have a maintenance dose of 20 mg (dose level 2). Dose level 1 is the minimum dose and dose level 2 is the maximum permitted dose in this group of patients
2. Participants with an eGFR  $>60$  mL/min/1.73m^2 will start with 20 mg (dose level 2) and have a maintenance dose of 40 mg (dose level 3). Dose level 1 is the minimum dose and dose level 3 is the maximum permitted dose in this group of patients.

The investigator is encouraged to up-titrate the dose of study intervention once the participant has been on a stable dose for 4 weeks ( $\pm 7$  days), either at the next regular visit or at an Up-titration Visit (see [Table 6-1](#)). Participants who do not tolerate their starting dose of 20 mg may be down-titrated at any point during the study, including between-scheduled visits if required for safety reasons. These participants may be up-titrated again based on the rules provided in [Table 6-1](#). If the participant is already at the minimum dose, the study intervention can be interrupted at the investigator's discretion as detailed in Section [6.6](#), based on blood potassium levels and renal function which will be monitored throughout the study.

#### Intake of study intervention

Participants will be instructed to take one tablet of study intervention, preferably in the morning, at approximately the same time each day. The study intervention should be taken with a glass of water, with or without food.

Note: On the day of the first PK visit (Month 3) the participant should be instructed not to take the tablet at home in the morning but to have the PK sample collected first and then to take the study intervention at the study site.

**Table 6–1 Dosage of Study Intervention for Administration**

eGFR value at the Baseline Visit, based on local laboratory results:	eGFR 25 to ≤60 mL/min/1.73m 		eGFR >60 mL/min/1.73m 	
Participant randomized to group:	Finerenone	Placebo	Finerenone	Placebo
Starting dose:	10 mg finerenone OD	Placebo OD (Dose Level 1)	20 mg finerenone OD	Placebo OD (Dose Level 2)
Maintenance dose:	20 mg finerenone OD	Placebo OD (Dose Level 2)	40 mg finerenone OD	Placebo OD (Dose Level 3)
Minimum dose after down-titration:	10 mg finerenone OD	Placebo OD	10 mg finerenone OD	Placebo OD
Maximum dose after up-titration:	20 mg finerenone OD	Placebo OD	40 mg finerenone OD	Placebo OD
Study intervention intake	One tablet of study intervention OD, preferably in the morning at approximately the same time each day. Note: Study intervention will be administered at home, except on the day of the first PK visit when the tablet will be taken at the study site			
Missed intake	
 
If discovered within 16 hours after the scheduled time, the participant should take one tablet of study intervention as soon as possible
 
If discovered >16 hours after the scheduled time, this will be considered to be a 'missed' dose and the participant should wait and take the next tablet of study intervention at the usual (scheduled) time.
 
			
Up-titration of dose	
Finerenone
 
 
Up-titrate study intervention to the next possible higher dose based on serum/plasma potassium level
 
eGFR decrease is <30% compared to last scheduled visit.
 
 
Placebo
 
 
Sham-titrate.
 
			
Down-titration of dose	
 
If potassium ≥5.5, down-titrate to the next lower dose level in a step-wise manner (dose level 2 to 1, or dose level 3 to 2)
 
If at dose level 1, interrupt study intervention treatment; study intervention should be re-introduced at dose level 1 as soon as the investigator considers it to be medically justified without compromising safety
 
If in the opinion of the investigator, the participant cannot tolerate the maximum dose level of study intervention, the study intervention dose may be reduced to the next lower dose level.
 
			

Abbreviations: eCRF = electronic case report form; eGFR = estimated glomerular filtration rate; OD = once daily, PK = pharmacokinetics

\* NOTE: Potassium and eGFR according to local laboratory values

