**Please note:**

- 1 month corresponds to 30 days
- Study visits should occur as close as possible to the specified time points in the protocol, but time windows are permitted as specified in the SoA
- At any scheduled or unscheduled visit, the dose of study intervention may be increased to the next possible higher dose, based on serum/plasma potassium level analyzed in the local laboratory and provided the participant was already on a stable dose for 4 weeks ±7 days.

Abbreviations: AE = adverse event; CKD-EPI = Chronic Kidney Disease Epidemiology Collaboration; D = Day; eGFR = estimated glomerular filtration rate; ECG = electrocardiogram; EOS = end-of-study; EQ-5D-5L = EuroQoL Group 5-dimension 5-level questionnaire; hs-TnT = high-sensitivity troponin-t; IxRS = interactive voice / web response system; med. = medication; KCCQ = Kansas City Cardiomyopathy Questionnaire; M = Month; NT-proBNP = n-terminal prohormone B-type natriuretic peptide; NYHA = New York Heart Association; O = on-site; PGIC = Patient Global Impression of Change; PGIS = PGI of Severity; PD = premature discontinuation; PT = post-treatment; SoA = schedule of activities; Tel. = telephone

- Randomization has to occur within 2 weeks of the Screening Visit. If the Screening Visit and Visit 1 (Day 1, Baseline) are performed on the same day, procedures listed for both visits are to be performed only once.
- Study visits to be conducted as a clinic visit or a telephone contact visit. These visits will alternate at 4-monthly intervals from Month 12 onwards with participant contact being made every 2 months.
- This visit should be performed for safety check after any up-titration (4 weeks ±7days) and after restart of study intervention following an interruption for >7 consecutive days. A full unscheduled safety visit should be performed within an adequate timeframe proposed by the investigator after down-titration for reasons other than hyperkalaemia, otherwise only potassium is to be rechecked (refer to [Table 6–1](#))

- d The PD Visit should take place as soon as possible but within 7 days after the last intake of study intervention. If the PD Visit cannot be performed within the timeframe specified, no PD Visit is required. All randomized participants will be followed until the study ends, even if they did not take study intervention or permanently discontinued study intervention.

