**Caution**

Concomitant use of finerenone in combination with weak or moderate CYP3A4 inhibitors such as: amiodarone, aprepitant, bicalutamide, chloramphenicol, dasatinib, imatinib, lapatinib, mifepristone, nilotinib, norfloxacin, tacrolimus, or verapamil increases finerenone exposure. Additional serum potassium monitoring should be considered, and make finerenone treatment decisions as directed in [Table 6–2](#). More examples of weak or moderate CYP3A4 inhibitors will be provided separately.

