## 6.6 Dose Modification

As described in Sections [6.6.1](#) and [4.3](#), the dose of study intervention should be adjusted (up-or down-titration) on the basis of potassium and eGFR levels.

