### 6.6.1 Monitoring of Blood Potassium and Dose Adjustment

Guidance for the adjustment of dose after start of study intervention intake based on serum/plasma potassium levels is provided in [Table 6–2](#).

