**Table 6–2 Potassium Levels and Guidance for Dose Adjustment**

Serum / plasma potassium (K + mmol/L)	Action to be taken
First sample:	
<5.0	Increase to the next higher dose level (or continue at maximum permitted dose level)
≥5.0 to <5.5	Continue the current dose level
≥5.5 to <6.0	Down-titrate to the next lower dose if possible; if patient is already on dose level 1, interrupt study intervention. K + should be re-checked within 72 h of initial K + result awareness; follow option a
≥6.0	Interrupt study intervention and K + should be re-checked within 72 h of initial K + result awareness; follow option b
Second and subsequent sample:	
Option a <5.5	Continue current dose
≥5.5	Down-titrate to the next lower dose if possible, or interrupt study intervention and recheck K +
Option b <5.5	Restart at dose level 1
≥5.5	Continue to withhold study intervention, further monitoring of K + . Restart at dose level 1 ONLY if K + is <5.0 mmol/L

The following aspects have also to be taken into consideration:

1. If the participant is already on dose level 1 no further decrease is possible after interruption, the same dose level should be re-started once serum/plasma potassium falls below 5.5 mmol/L. Serum/plasma potassium is to be measured at a safety visit 4 weeks ± 7 days after re-starting treatment or dose adjustment.
2. If the participant is on dose level 1 of study intervention, but hyperkalemia recurs soon after a previous event of hyperkalemia leading to interruption of study intervention, and there is no explanation for the recurring hyperkalemia event other than intake of study intervention, premature and permanent discontinuation of study intervention is recommended.
3. In case of hyperkalemia, it is at the investigator's discretion to take measures, including treatment and monitoring in accordance with local practice standards, beyond those reflected in [Table 6–2](#).

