### Local Laboratory Assessment

Blood safety samples will be taken from the Screening Visit onwards for analysis at the local laboratory.

- The following clinical chemistry parameters must be measured and the values documented in the eCRF
  - Serum/plasma creatinine (eGFR will be calculated automatically in the eCRF using the CKD-EPI formula)
  - Serum/plasma potassium.

From visit 2 (Month 1) onwards, study participants may have their local laboratory assessments taken up to 3 days prior to the study visit.

Potassium values should be recorded using a single decimal point (e.g. 4.5 mmol/L or mEq/L). In the event of hyperkalemia, please see [Table 6–2](#) for guidance.

Up-titration or down-titration of the study intervention will be based on local potassium results and must be documented in the eCRF. Down-titration of the study intervention should occur primarily for safety reasons but can also be done for exceptional logistical reasons (e.g. study intervention supply issue).

Additionally, at screening, BNP or NT-proBNP can be measured if not available from clinical medical records.

In women of childbearing potential, a pregnancy test will be performed locally, at screening and baseline. Further pregnancy tests should be performed in participants of childbearing potential as required by national/institutional regulations (e.g. at every visit). At any time during study participation, additional pregnancy testing should be performed upon suspicion of pregnancy. Both serological and urine tests are acceptable.

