## 10.2 Appendix 2: Clinical Laboratory Tests

- The tests detailed in [Table 10–1](#) will be performed by the central laboratory.
- In addition to samples for the central laboratory, other blood safety samples will be taken from the Screening Visit onwards for analysis at the local laboratory. These samples will be taken only as long as the participant has not prematurely and permanently discontinued study intervention. From visit 2 (Month 1) onwards, study participants may have their local laboratory tests taken up to 3 days prior to the study visit.
- eGFR (CKD-EPI) ([Horio et al. 2010](#), [Levey et al. 2009](#)) must be measured/calculated locally for as long as the participant is treated with the study intervention
- Up-titration or down-titration of the study intervention will be based on local potassium and must be documented in the eCRF. Down-titration of the study intervention will occur for safety reasons only.
- Potassium values should be recorded using a single decimal point (e.g. 4.5 mmol/L or mEq/L). In the event of hyperkalemia, please see Section [6.6.1](#) for guidance on treatment.
- Protocol-specific requirements for inclusion or exclusion of participants are detailed in Section [5](#) of the protocol.
- Additional tests may be performed at any time during the study as determined necessary by the investigator or required by local regulations.
- Pregnancy testing. Refer to Section [5.1](#) Inclusion Criteria for screening pregnancy criteria.

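### Table 6–1 sets no upper potassium limit on its one-level step-down, so at K+ ≥6.0 mmol/L it leaves dose levels 2 and 3 on drug where Table 6–2 interrupts it

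*Protocol*

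**What the plan says.** Table 6–1 (Protocol Section 6.1) gives this down-titration rule: "If potassium ≥5.5, down-titrate to the next lower dose level in a step-wise manner". It names the moves from level 2 to 1 and from level 3 to 2. Its next bullet interrupts drug, but only for a participant at level 1.

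Table 6–2 (Section 6.6.1) splits the same range. At 5.5 to <6.0 it steps down one level, or interrupts if the participant is at level 1. At ≥6.0 its entry begins "Interrupt study intervention and K", followed by a re-check within 72 hours and option b for restarting. That row carries no dose-level condition.

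Several places send potassium decisions to Table 6–2 or its section:

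- Section 6.6.1: "Guidance for the adjustment of dose after start of study intervention intake based on serum/plasma potassium levels is provided in" Table 6–2.
- Section 6.6, citing Sections 6.6.1 and 4.3: "the dose of study intervention should be adjusted (up-or down-titration) on the basis of potassium and eGFR levels".
- Section 6.5, on CYP3A4 inhibitors: "make finerenone treatment decisions as directed in" Table 6–2.
- Section 8.2.3, local laboratory: "In the event of hyperkalemia, please see" Table 6–2.
- Section 10.2: "In the event of hyperkalemia, please see Section" 6.6.1.
- Section 7.1 refers temporary interruption to Section 6.6.

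Other text leans towards Table 6–1. Section 4.1 (Treatment Period) says that participants with elevated potassium go down one dose, with no exception at 6.0, and SAP Section 3 repeats it. Footnote c of the Schedule of Activities says that after a down-titration for hyperkalaemia "otherwise only potassium is to be rechecked", and refers to Table 6–1, which contains no re-check rule.

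**The concern.** The two tables give different instructions for the same laboratory result, at the threshold that Protocol Section 9.4.2 labels severe hyperkalaemia. Section 2.3 names hyperkalaemia as an important identified risk and relies on potassium-based stopping and dose-reduction rules to contain it. Section 4.3 cites cohort evidence that hyperkalaemia raises the odds of death within a day, and reports potassium above 6 mmol/L in the earlier finerenone heart failure study, so the situation is realistic.

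Table 6–1 is not merely silent on interruption. It addresses interruption and reserves it for level 1, so it reads as a complete rule. A site that followed it at K+ ≥6.0 would keep a level 2 or level 3 participant on active drug when the protocol's own potassium table says to stop.

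**Working it through.** There is no sample-size, power or alpha figure to reproduce. The check sets the rules side by side.

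**Inputs.** Level 1 is 10 mg, level 2 is 20 mg and level 3 is 40 mg (Section 6.1). The dose rules are in Tables 6–1 and 6–2. The restart rules are option b and note 1 of Table 6–2, and Section 7.1.1.

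**Dose after the first sample**

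| K+ (mmol/L) | Dose level | Table 6–1 | Table 6–2 | Agree? |
|---|---|---|---|---|
| 5.5 to <6.0 | 1 | 0 mg | 0 mg | yes |
| 5.5 to <6.0 | 2 | 10 mg | 10 mg | yes |
| 5.5 to <6.0 | 3 | 20 mg | 20 mg | yes |
| ≥6.0 | 1 | 0 mg | 0 mg | yes |
| ≥6.0 | 2 | 10 mg | 0 mg | **no** |
| ≥6.0 | 3 | 20 mg | 0 mg | **no** |

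Two bands by three levels make 6 cells; 4 agree and 2 conflict, both at ≥6.0. Capping the Table 6–1 bullet at <6.0 and adding interruption at ≥6.0 makes all 6 agree.

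**Restart overlap at level 1.** Take a first K+ ≥6.0, a second sample ≥5.5 and a later value of 5.0 to 5.4.

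- Option b keeps drug withheld, because after a second sample ≥5.5 it allows restart only below 5.0.
- Note 1 under the same table restarts level 1 once potassium is below 5.5.
- The result is 0 mg against 10 mg. If the second sample is already below 5.5, both rules restart at 10 mg and nothing conflicts.

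**Restart overlap at level 3.** Take an interruption for K+ ≥6.0 that lasts more than 7 days. Section 7.1.1 lists hyperkalaemia among its reasons for interruption and restarts one level down.

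| Level before interruption | Option b | Section 7.1.1 |
|---|---|---|
| 1 | 10 mg | 10 mg (no lower level exists) |
| 2 | 10 mg | 10 mg |
| 3 | 10 mg | **20 mg** |

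One of 3 levels conflicts.

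**The case against.** The best defence is that Table 6–1 cannot be used alone to titrate on potassium. Its up-titration bullet gives no potassium value and it has no re-check rule, so a site must look elsewhere. Section 6.6.1 assigns potassium-based dosing to Table 6–2, and Section 7.1 assigns interruption, the very action in dispute, to Section 6.6. Note 3 under Table 6–2 leaves the investigator free to do more, and Section 7.1 requires discontinuation if the investigator judges continued treatment harmful. On restart, option b is the specific rule for K+ ≥6.0, while note 1 and Section 7.1.1 are general.

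Most of this stands. It makes Table 6–2 the evident governing table and largely settles the restart overlaps in favour of option b. It does not remove the contrary rule. The step-down half of Table 6–1 does carry a number, 5.5, and can be acted on as it stands; Section 4.1 and SAP Section 3 echo it without a cap; and no sentence gives precedence. Investigator discretion permits the right action but does not resolve two conflicting instructions.

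The strength of the case should not be measured by counting cross-references. Sections 6.1 and 7.1.1 also point to Table 6–1 for titration or monitoring visits, so such a count depends on what is included.

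**Conclusion.** The inconsistency is real and should be corrected. At K+ ≥6.0 the two tables differ for dose levels 2 and 3, by 10 mg and 20 mg against no drug. The restart overlaps are minor: each affects one dose level after one particular sequence of events.

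A reader might infer that the trial has no stopping rule for severe hyperkalaemia, or that participants were kept on drug at K+ ≥6.0. The documents do not support either. The correct rule is in Table 6–2 and is signposted, and nothing in the documents shows which table sites followed. Nor do they give an expected frequency of K+ ≥6.0 in this trial, so no number of affected participants can be estimated. No effect on the treatment comparison, the alpha level or power is claimed.

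The conclusion rests on two things: the reading that Table 6–2 is meant to govern, which is an inference from the cross-references, and the text of Amendment 2. The SAP is based on a protocol amendment dated 26 October 2022 that is not available here, and that amendment may already have changed the wording.

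**What to change.** First check the 26 October 2022 amendment. If the wording persists, make four edits:

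1. **Table 6–1, first down-titration bullet.** Limit the one-level step-down to potassium of 5.5 to <6.0, and add that at ≥6.0 drug is interrupted at any dose level, with a reference to Table 6–2.
2. **Schedule of Activities, footnote c.** Add Table 6–2 beside Table 6–1 for the potassium re-check. Keep the Table 6–1 reference, because the footnote also covers down-titration for other reasons and only Table 6–1 has the tolerability bullet.
3. **Note 1 under Table 6–2.** Limit only the restart sentence to interruptions at 5.5 to <6.0, where it supplies the restart rule that option a lacks. Leave the second sentence, on the potassium check 4 weeks ± 7 days after restart or dose adjustment, applying to all cases. Footnote c and Section 7.1.1 tie the restart visit to interruptions of more than 7 days, so limiting the whole note could drop that check after an early restart following K+ ≥6.0.
4. **Section 7.1.1.** Add an exception: after an interruption for K+ ≥6.0, restart is at dose level 1 as in Table 6–2.

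The cost is a protocol amendment, since these are dosing instructions and a site memo alone would not suffice. Section 10.1.1 requires ethics committee approval for amendments that change the study design and authority approval for substantial ones, and the country-specific versions would need to match. Bundling the edits with the next amendment and sending sites a clarification keeps the burden small. No extra visits, samples or participants are needed.
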